6.3 Demographic and Baseline Characteristics

Demographic information (age, sex, ethnicity, race) will be summarized on the safety, full, and PP analysis sets. Baseline data pertaining to habitual lens (lens brand, power, [REDACTED] [REDACTED]) will be summarized on the full and PP analysis sets.

6.4 Effectiveness Analyses

This study defines one primary effectiveness endpoint, [REDACTED] [REDACTED] The FAS will serve as the primary set for all effectiveness analyses. [REDACTED] [REDACTED]

6.4.1 Primary Effectiveness

The primary objective of this study is to demonstrate noninferiority in VA of DD T2 when compared to MYDAY.

The primary endpoint is VA (logMAR) at Dispense and Week 1, Follow-Up.

6.4.1.1 Statistical Hypotheses

The null and alternative hypotheses are formulated in terms of the predefined margin of 0.05 for noninferiority:

$$H_0: \mu_{(DDT2)} - \mu_{(MYDAY)} \geq 0.05$$

$$H_a: \mu_{(DDT2)} - \mu_{(MYDAY)} < 0.05$$

where $\mu_{(DDT2)}$ and $\mu_{(MYDAY)}$ denote the mean VA for DD T2 and MYDAY, respectively.

6.4.1.2 Analysis Methods

A mixed effect repeated measures model will be utilized to test these hypotheses. The model will include terms for lens, visit, lens by visit interaction, period, and sequence. Within-subject correlation due to eye and the crossover will also be accounted for in the model. Lens difference (DD T2 minus MYDAY) and the corresponding one-sided 95% upper confidence limit will be computed. Noninferiority in VA will be declared if upper confidence limit is less than 0.05.

6.4.2 Secondary Effectiveness

Not applicable.

[figure not shown]
6.4.2.1 Statistical Hypotheses

Not applicable.

6.4.2.2 Analysis Methods

Not applicable.

[figure not shown]

6.5 Subgroup Analyses

It is not expected that demographic or baseline characteristics will have an impact on the results in this study. No subgroup analyses are planned.

6.6 Handling of Missing Data

All data obtained in evaluable subjects/eyes will be included in the analysis. No imputation for missing values will be carried out for the primary analysis.

6.8 Safety Analysis

The safety endpoints for this study are AEs, biomicroscopy findings, and device deficiencies.

Descriptive summaries (counts and percentages) for ocular and nonocular AEs will be presented by Medical Dictionary for Regulatory Activities Preferred Terms. AEs leading to study discontinuation, significant nonserious AEs, and SAEs will be identified. Individual subject listings will be provided, as necessary.

Individual subject listings will be provided for AEs that occur after signing informed consent but prior to exposure to study lenses. This listing will include the following variables: lens sequence assigned, Investigator, subject, age, sex, eye (if ocular), in addition to relevant data describing the AE.

[figure not shown]
Each biomicroscopy parameter will be tabulated by its grade. For each biomicroscopy parameter, counts and percentages of eyes that experience an increase of ≥ 2 grades from baseline (Visit 1) to any subsequent visit within the specific crossover period will be presented. A supportive listing will be generated which will include all biomicroscopy data from all visits within the affected period for these eyes experiencing the increase, with the following variables: lens, Investigator, subject, age, sex, visit, eye, parameter, baseline value, and value at the visit.

Two listings (prior to exposure of study lenses and treatment-emergent) of device deficiencies, as recorded on the Device Deficiency Form, will be provided. Additionally, each device deficiency category will be tabulated. Each listing will include the following variables: lens, Investigator, subject, age, sex, in addition to relevant data describing the device deficiency and associated ADE, if any.

No inferential testing will be done for safety analysis.

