Exclusion Criteria	
 1. Any anterior segment infection, inflammation, or abnormality or disease (including systemic) that contraindicates contact lens wear, as determined by the Investigator. 2. Any use of systemic or ocular medications for which contact lens wear could be contraindicated, as determined by the Investigator. 3. History of refractive surgery or plan to have refractive surgery during the study or irregular cornea in either eye. 4. Ocular or intraocular surgery (excluding placement of punctal plugs) within the previous 12 months or planned during the study. 5. Biomicroscopy findings at screening that are moderate (Grade 3) or higher and/or corneal vascularization that is mild (Grade 2) or higher. 6. Current or history of pathologically dry eye in either eye that, in the opinion of the Investigator, would preclude contact lens wear. 7. Current or history of herpetic keratitis in either eye. 8. Eye injury in either eye within twelve weeks immediately prior to enrollment for this trial. 9. Any previous or current wear of MYDAY. 10. Habitually wearing monovision or multifocal lenses during the last 3 months. 11. Current or history of intolerance, hypersensitivity or allergy to any component of the study products. 12. Wearing habitual contact lenses in an extended wear modality (routinely sleeping in lenses for at least 1 night per week) over the last 3 months prior to enrollment. 13. Any use of topical ocular medications and artificial tear or rewetting drops that would require instillation during contact lens wear. 14. The Investigator, his/her staff, family members of the Investigator, family members of the Investigator's staff, or individuals living in the households of the

	
aforementioned persons may not participate in the study.
 
15. Participation of the subject in a clinical trial within the previous 30 days or currently enrolled in any clinical trial.

Associated Materials	Lubrication/re-wetting drops will not be permitted.

Table 1-1

Schedule of Study Procedures and Assessments

Procedure/ Assessment	Visit 1, Day 1: Baseline/Dispense Study Lens 1	Visit 2, Week 1: 6 Days (\pm 1 day) Follow-up Study Lens 1 / Dispense Study Lens 2	Visit 3, Week 2: 6 Days (\pm 1 Day) Follow-up Study Lens 2/ Exit
Informed Consent	✓	-	-
Demographics	✓	-	-
Medical History	✓	-	-
Concomitant Medications	✓	✓	✓
Inclusion/Exclusion	✓	-	-
Habitual lens (brand, power)	✓	-	-

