15	Assess and record any AEs and device deficiencies reported or observed during the study visit. Note: AEs and device deficiencies must be recorded for all enrolled subjects from the time of signature of informed consent including those that screen fail.
16	Dispense study lenses and instruct the subject on lens wear.
17	Schedule Visit 2 to take place 6 days (\pm 1 day) after Visit 1.

5.1.2 Visit 2 (6 Days \pm 1 Day) – Follow-up Study Lens 1 / Dispense Study Lens 2

1	Obtain information on any changes in medical health and/or the use of concomitant medications.
2	Record any device deficiencies or AEs that are observed or reported, including those associated with changes in concomitant medication dosing since the previous visit(s).
3	Review subject compliance with lens wear.
4	[REDACTED]
5	Evaluate the study lenses by performing the following: • Snellen VA with study lenses (OD and OS, at distance) Note: Perform BCVA if there is a decrease of VA by 2 lines or more with IP

[figure not shown]
6	
7	
8	Have subject remove study lenses.
9	Perform slit-lamp biomicroscopy (without contact lenses) to evaluate the following: 
• Limbal hyperemia• Bulbar hyperemia• Corneal staining• Conjunctival staining• Corneal vascularization• Corneal epithelial edema• Corneal stromal edema• Conjunctival compression/indentation• Chemosis• Palpebral conjunctival observations• Corneal infiltrates• Other findings
10	Based upon the randomized treatment sequence assignment, have the subject insert the appropriate study lenses to be evaluated. 
• Keep all lidding foils of lenses used during lens fit process for study lens accountability.• Follow procedures to maintain masking.
11	
12	Evaluate the study lenses by performing the following: 
• Snellen VA with study lenses (OD and OS, at distance)*• Over-refraction if necessary to determine the best contact lens-corrected VA and final study lens power(s) 
*VA w/study lenses must be 20/40 OU or better for subject to leave the office

13	
14	
15	Schedule Visit 3 to take place 6 days ± 1 day after Visit 2.

5.1.3 Visit 3 (6 Days ± 1 Day) - Follow-up Study Lens 2 / Exit Visit

1	Obtain information on any changes in medical health and/or the use of concomitant medications.

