6.2 Analysis Data Sets

6.2.1 Safety Analysis Set

Safety analyses will be conducted using the safety analysis set on a treatment-emergent basis. As such, the safety analysis set will include all subjects/eyes exposed to any study lenses evaluated in this study. For treatment-emergent safety analyses, subjects/eyes will be categorized under the actual study lenses exposed.

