5.3 Statistical Methods for Safety Analyses

The analysis set for all safety analyses is the safety analysis set as defined in Section 2.1. Baseline will be defined as the last measurement prior to exposure to investigational product, Visit 1. Safety variables will be summarized descriptively.

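### Biomicroscopy rises of 2 grades or more in period 2 are measured only from Visit 1, so changes on lens 1 and lens 2 are not separated; one added Visit 2-referenced display would show this cheaply

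*Protocol*

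**What the plan says.** Protocol 6.8 plans, for each biomicroscopy parameter, the number and percentage of eyes with an "increase of ≥ 2 grades from baseline (Visit 1) to any subsequent visit within the specific crossover period will be presented". SAP 5.3 applies one baseline to all safety variables: "Baseline will be defined as the last measurement prior to exposure to investigational product, Visit 1". SAP 5.3.2 names the matching table and listing. It also plans a table of grade frequencies at each visit and separate listings for infiltrates and other findings.

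The supporting listing in Protocol 6.8 covers "all biomicroscopy data from all visits within the affected period for these eyes experiencing the increase", with a single baseline value. Neither document says whether the Visit 2 examination counts as a visit of period 2.

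Under Protocol 6.2.1, "subjects/eyes will be categorized under the actual study lenses exposed". Together with the lens variable in the listing, this implies a table laid out by lens. That is an inference: neither Protocol 6.8 nor the SAP table title says so.

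Protocol 5.1.2 fixes the order of events at Visit 2:
- step 8: "Have subject remove study lenses"
- step 9: "Perform slit-lamp biomicroscopy (without contact lenses) to evaluate the following"
- step 10: "have the subject insert the appropriate study lenses to be evaluated"

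There is no washout. Exclusion criterion 5 in the protocol synopsis bars "Biomicroscopy findings at screening that are moderate (Grade 3) or higher and/or corneal vascularization that is mild (Grade 2) or higher". Visit 1 grades can therefore be as high as 2, or 1 for corneal vascularization.

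**The concern.** The count is confined to a crossover period and grouped by the lens worn, yet in period 2 the change is measured across the wear of both lenses. A finding that arose on lens 1 and is still present at Visit 3 is counted again under lens 2. A rise on lens 2 that follows a fall on lens 1 may not be counted at all. The grade just before lens 2 is already collected, so the two situations could be told apart.

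At stake is how readable the descriptive safety comparison is. Protocol 3.1 says the trial is meant to inform product development, and a reader of the planned table could not tell in which period a lens 2 entry arose.

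**Working it through.** The documents give no biomicroscopy event rates, so there is no planned figure to reproduce. The check is an enumeration of possible grade paths.

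**Inputs and assumptions.** V1, V2 and V3 are an eye's grades at Visits 1, 2 and 3. V1 is 0 to 2 (0 to 1 for vascularization) by exclusion criterion 5. Integer grades from 0 to 4 are assumed, since the readable text does not give the top of the scale; the count is repeated with a top grade of 3. Only scheduled visits are used. The Visit 2 examination is taken to close period 1, and Visit 3 to belong to period 2.

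**Rules.**
- Flagged in period 1: V2 − V1 ≥ 2
- Flagged in period 2, as planned: V3 − V1 ≥ 2
- Rise on lens 2: V3 − V2 ≥ 2

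| V1 range, top grade | Paths | Flagged in period 2 | Of these, rise ≥ 2 on lens 2 | Of these, no such rise | Of the latter, also flagged in period 1 | Rise ≥ 2 on lens 2, not flagged |
|---|---|---|---|---|---|---|
| 0–2, top 4 | 3×5×5 = 75 | 30 | 14 | 16 | 13 | 4 |
| 0–1 (vascularization), top 4 | 2×5×5 = 50 | 25 | 11 | 14 | 12 | 1 |
| 0–2, top 3 | 3×4×4 = 48 | 12 | 5 | 7 | 5 | 4 |

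These are counts of possible paths, not frequencies. They show what can happen, not how often.

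**Counted under lens 2 without a 2-grade rise on it (first row).** Of the 16 paths, 10 show no rise at all on lens 2 (such as 0-2-2) and 6 rise by one grade. All 10 are also flagged in period 1, because V2 ≥ V3 ≥ V1 + 2. So are three of the six (0-2-3, 0-3-4, 1-3-4). The other three (0-1-2, 1-2-3, 2-3-4) have no period 1 entry. Their Visit 2 grade is listed only if Visit 2 counts as a period 2 visit.

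**Omitted.** If V3 − V2 ≥ 2 and V3 − V1 ≤ 1, then V2 ≤ V3 − 2 ≤ V1 − 1, so the grade must first have fallen in period 1. With V1 at most 2, the only such paths are 1-0-2, 2-0-2, 2-0-3 and 2-1-3. None is flagged in period 1. One returns to the Visit 1 grade; the other three end one grade above it.

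**Where omitted eyes still appear.** Protocol 7.1 makes corneal staining at Grade 3 or higher, and neovascularization at Grade 2 or higher, reportable as Significant Nonserious AEs. SAP 5.3.1 tabulates these.
- Corneal vascularization: the only possible omitted path, 1-0-2, ends at Grade 2 and is reportable, if neovascularization means this parameter.
- Corneal staining: 2-0-3 and 2-1-3 are reportable under this rule; 1-0-2 and 2-0-2 are not.
- Infiltrates and other findings have their own listings in SAP 5.3.2.
- Other graded parameters, such as hyperemia and conjunctival staining, appear only if the investigator judges the change clinically relevant (Protocol 7.2).

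The by-visit frequency table does not help, because it shows no within-eye change.

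**Scale.** With 44 completers there are 44 × 2 = 88 eyes per lens. At 1:1 allocation, about 44 of them (22 subjects) wear that lens in period 2. One eye is 1/88 = 1.1%. As an illustration with assumed rates only, let lens A cause such rises in a proportion p of eyes, lens B in none, and a proportion q of the rises persist to Visit 3. Lens B is then charged with 44 × p × q eyes. For p from 2% to 10% and q from 25% to 100%, this runs from 44 × 0.02 × 0.25 = 0.22 eyes (0.25% of 88) to 44 × 0.10 × 1 = 4.4 eyes (5.0%). With q = 0 it is zero.

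**The case against.** Visit 1 is the only examination before any study lens is worn, both documents name it consistently, and Visit 2 comes after about 6 days on lens 1. A common unexposed reference is a defensible choice. That stands, and it is why the Visit 1 table should stay.

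A reader might infer that the table assigns changes to the wrong lens in both directions. The documents do not support that. The four paths with an earlier fall are left out, not moved to the other lens, and 2-0-2 only returns to its starting grade. Nor is every lens 2 entry without a 2-grade rise on lens 2 an error: 0-1-2 did rise on lens 2 and ended 2 grades above the unexposed value.

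A reader might also take 16 of 30 paths as an error rate. It is not one, because the paths are not equally likely.

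The mandatory reporting in Protocol 7.1 and the separate listings narrow the gap further. Figures next to the relevant text in both documents are not shown, so a further display may exist; this point rests on the readable text.

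**Conclusion.** The point holds as a minor, optional improvement. In period 2 the planned table combines change on both lenses. Eyes with a persisting lens 1 rise are counted again under lens 2, mostly with a matching period 1 entry. Four kinds of path with a rise on lens 2 are absent from the table and its listing. After the other reporting routes are allowed for, the remaining gap lies mainly in graded parameters such as hyperemia and conjunctival staining.

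The size and direction of any effect on the between-lens rates are unknown. The effect is zero if no lens 1 rise persists to Visit 3 and no grade falls in period 1. The documents do not support a conclusion that the safety comparison is biased or that the Visit 1 baseline is an error. SAP 5.2 states no safety hypotheses, Protocol 6.8 rules out inferential testing, and the noninferiority conclusion on visual acuity does not depend on these data.

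The verdict assumes a by-lens layout and that Visit 3 is the only scheduled period 2 examination after lens 2 has been worn.

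**What to change.** - Keep the Visit 1-referenced table and listing as planned.
- In the listing, show the pre-insertion Visit 2 grade for every eye flagged in period 2. This is how a 0-2-2 eye is recognized; it does not appear in the added display.
- Add one supplementary period 2 display, by lens, of rises of 2 grades or more from the Visit 2 examination, and list the eyes it flags.
- Footnote that Visit 2 is a post-lens-1 value, so this display misses stepwise rises (0-1-2), can flag a return to the Visit 1 grade (2-0-2), and cannot show whether lens 2 sustained a finding.

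The cost is one table with its listing, one listing column and a footnote, all from data already collected and with no change to visits. The downside is a second descriptive table to read beside the first, based on about 22 completers per lens.

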6.9 Interim Analyses

There are no plans to conduct an interim analysis and no criteria by which the study would be terminated early based upon statistical determination.

7 ADVERSE EVENTS AND DEVICE DEFICIENCIES

Terms and Definitions

Adverse Event (AE)	Any untoward medical occurrence, unintended disease or injury, or untoward clinical signs (including abnormal laboratory findings) in subjects, users or other persons, whether or not related to the investigational medical device (test article). Note: For subjects, this definition includes events related to the test article, the control article, or the procedures involved. For users or other persons, this definition is restricted to events related to the test article.
Adverse Device Effect (ADE)	AE related to the use of an investigational medical device (test article) or control article. Note: This definition includes AEs resulting from insufficient or inadequate instructions for use, deployment, implantation, installation, or operation; any malfunction; and use error or intentional misuse of the test article or control article.
Anticipated Serious Adverse Device Effect (ASADE)	Serious ADE which by its nature, incidence, severity or outcome has been identified in the risk management file.

Device Deficiency	Inadequacy of a medical device with respect to its identity, quality, durability, reliability, safety, or performance. Note: This definition includes malfunctions, use errors, and inadequate labeling.
Malfunction	Failure of a medical device to meet its performance specifications or otherwise perform as intended. Performance specifications include all claims made in the labeling of the device. The intended performance of the device refers to the intended use for which the device is labeled or marketed.
Nonserious Adverse Event	AE that does not meet the criteria for an SAE.
Serious Adverse Event (SAE)	
AE that led to any of the following:
 
 • Death. • A serious deterioration in the health of the subject that either resulted in: 
 a) a life-threatening illness or injury. Note: Life-threatening means that the individual was at immediate risk of death from the event as it occurred, ie, it does not include an event which hypothetically might have caused death had it occurred in a more severe form. b) any potentially sight-threatening event or permanent impairment to a body structure or a body function. c) in-patient hospitalization or prolonged hospitalization. Note: Planned hospitalization for a pre-existing condition, without serious deterioration in health, is not considered an SAE. In general, hospitalization signifies that the individual remained at the hospital or emergency ward for observation and/or treatment (usually involving an overnight stay) that would not have been appropriate in the physician's office or an out-patient setting. Complications that occur during hospitalization are adverse events. If a complication prolongs hospitalization or fulfills any other serious criteria, the event is serious. When in doubt as to whether "hospitalization" occurred, the event should be considered serious. d) a medical or surgical intervention to prevent a) or b). e) any indirect harm as a consequence of incorrect diagnostic test results when used within manufacturer's instructions

	
for use.
 
 • Fetal distress, fetal death, or a congenital abnormality or birth defect. 
Refer to Section 7.1 for additional SAEs.

Serious Adverse Device Effect (SADE)	ADE that has resulted in any of the consequences characteristic of an SAE.
Significant Nonserious Adverse Event	A significant nonserious AE is a symptomatic, device-related, non-sight threatening AE that warrants discontinuation of any contact lens wear for greater than or equal to 2 weeks. Refer to Section 7 for additional Significant Nonserious AEs.
Unanticipated Serious Adverse Device Effect (USADE)	Serious adverse device effect which by its nature, incidence, severity or outcome has not been identified in the risk management file.
Use Error	Act or omission of an act that results in a different medical device response than intended by manufacturer or expected by user. Note: This definition includes slips, lapses, and mistakes. An unexpected physiological response of the subject does not in itself constitute a use error.

7.1 General Information

An AE is any untoward medical occurrence, unintended disease or injury, or untoward clinical signs (including abnormal laboratory findings) in subjects, users, or other persons, whether or not related to the investigational medical device (test article).

Figure 7-1

Categorization of All AEs

[figure not shown]
[figure not shown]

Figure 7-2

Categorization of All Serious Adverse Events

Serious Adverse Events

In addition to reporting all AEs (serious and nonserious) meeting the definitions, the Investigator must report any occurrence of the following as an SAE:

- An ocular infection including a presumed infectious ulcer with any of the following characteristics:
 - Central or paracentral location
 - Penetration of Bowman's membrane

- Infiltrates > 2 mm diameter
- Iritis
- Increase in intraocular pressure
- Culture positive for microorganisms
- Increasing size or severity at subsequent visits
- Any central or paracentral corneal event (such as neovascularization) that results in permanent opacification
- Hypopyon
- Hyphema
- Neovascularization within the central 6 mm of the cornea
- Permanent vision loss as defined by loss of 2 or more lines of BCVA from enrollment visit that fails to resolve
- Uveitis (anterior, intermediate, or posterior)
- Corneal abrasion affecting \geq 50% of corneal surface area

Significant Nonserious Adverse Events

A significant non-serious AE is a symptomatic, device-related, non-sight threatening AE that warrants discontinuation of any contact lens wear for greater than or equal to 2 weeks. In addition, the Investigator must report any occurrence of the following as a Significant Nonserious AE:

- Peripheral non-progressive non-infectious ulcers
- All symptomatic corneal infiltrative events
- Corneal staining score greater than or equal to Grade 3 [Grading scale is based upon ISO 11980:2012 unless otherwise specified]
- Temporary vision loss as defined by loss of 2 or more lines of BCVA from enrollment visit that persists for 2 or more weeks
- Neovascularization score greater than or equal to Grade 2 [Grading scale is based upon ISO 11980:2012 unless otherwise specified]

The above events are based upon the categories provided in the ISO 11980 and the US FDA Premarket Notification (510(k)) Guidance Document for Daily Wear Contact Lenses and Contact Lens Care Products.

Device Deficiencies

A device deficiency is inadequacy of a medical device with respect to its identity, quality, durability, reliability, safety, or performance. A device deficiency may or may not be associated with patient harm (ie, ADE or SADE); however, not all ADEs or SADEs are due to a device deficiency. The Investigator should determine the applicable category listed in the Device Deficiency eCRF for the identified or suspect device deficiency and report any patient harm separately. Examples of device deficiencies include the following:

- Failure to meet product specifications (eg, incorrect lens power/diameter/base curve/color)
- Lens cloudy
- Lens surface/edge defect
- Torn lens during handling/in pack
- Packaging deficit (eg, mislabeled product)
- Suspect product contamination
- Lack of performance

